#### 9.2.4.1 Prescribers

Prescribers who consent to participate in these types of surveys will be first contacted by email, then by phone if they do not respond to the email. Their recruitment will be done as follows:

Template No.: RWI\_TP\_EPI0016 Revision 1 Reference: RWI\_WI\_EPI0005

Protocol/Study No: SC02 EMA/2018/19/PE

Page 32 of 92

- Prescribers will be invited to participate in the survey via email. The email invitations will contain the link to the web questionnaire. In the invitation, the survey background and objectives, the contact information for questions, and the proposed compensation will be explained to the prescribers at this step. Compensation will be compliant with relevant guidelines of each country and will compensate the actual effort and time needed to fill out the questionnaire.
- If the questionnaire is not completed, the prescribers will be sent a reminder by email one week after the invite was sent out.
- If the target is not achieved, a second reminder by phone will be conducted approximately 1.5 weeks after the invite was sent out.
- If the questionnaire is still not completed, a third reminder will be sent to the prescribers by email approximately 3 weeks after the invite was sent out.

If necessary, i.e. if the target number of responders is still not reached, recruitment will attempt to continue to achieve the targeted study sample size. A prescriber will be considered unreachable if he/she has been contacted between 3 to 5 times without an answer.

For each prescriber selected, the number of times the prescriber was contacted, as well as the date and time when he/she completed the web questionnaire, will be recorded. The recruitment in each target country will be stopped when the target number is reached (see Section 9.2.1.1 for further details on prescriber selection.

The number of prescribers that are eligible for inclusion in the study and the survey response rate will be monitored regularly.

The IQVIA internal field team will support prescribers if they see that the prescribers get stuck during the course of completing the survey, or if the prescribers stop for any reason – they will provide technical help. A free phone number will also be available for prescribers to call.

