# 9.2.4 Study Enrolment

The following groups will be considered as the target population:

- All prescribers within the selected specialties in the selected countries who have prescribed a weekly dose of MTX in the past 3 months
- All pharmacists in the selected countries who have dispensed a weekly dose of MTX in the past 3 months
- All patients in the selected countries who have used a weekly dose of MTX in the past 3 months

The survey will be conducted by IQVIA's Global Primary Intelligence, a division of IQVIA specialised in the conduct of phone and web surveys for more than 20 years. IQVIA's Global Primary Intelligence will create a web-based survey. Prescribers, pharmacists and patients' answers/data will be collected through this web survey. Participants will be randomly contacted, mainly by email, and phone or letter when needed, according to their stratum.

The targeted prescribers will be randomly selected and enrolled on an ongoing basis until the study size is reached (37). Random selection of prescribers and pharmacists is performed to minimise selection bias.

An equal distribution of age, gender and indication for MTX treatment cannot be made throughout recruitment, but a quota can be built into the survey to allow certain numbers for each of these categories. However, this may result in a longer period of recruitment and lower number of respondents. If this is the case, we will remove the quota at some point during the fieldwork, to recruit the pre-defined sample size. It should also be noted that the survey was not designed to provide a representative sample across age categories, gender, or indication for MTX.

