### 9.9 Limitations of Research Methods

#### 9.9.1 Bias

#### Selection bias:

#### a) Prescribers

The potential for selection bias of prescribers participating in a survey is an inherent limitation to any study based on volunteer participation. For instance, it is possible that prescribers willing to participate in the study will have the highest awareness of risks associated with use of MTX. To quantify the selection bias, the distribution of sociodemographic characteristics of prescribers (country, specialty, years of practice, gender etc.) will be compared between participants and non-participants.

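### Prescriber recruitment stops at the country target and the phone reminder is made only if the target is unmet, so the sample may be weighted towards early email responders

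*Protocol*

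**What the plan says.** Section 9.2.4 of the protocol says of prescribers that they are "randomly selected and enrolled on an ongoing basis until the study size is reached". It gives the reduction of selection bias as the reason for random selection.

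Section 9.2.4.1 sets out the contact sequence:

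- The opening sentence says prescribers are "first contacted by email, then by phone if they do not respond to the email". The trigger is the individual's own non-response.
- At one week: "If the questionnaire is not completed, the prescribers will be sent a reminder by email one week after the invite was sent out". This trigger is also individual.
- At 1.5 weeks: "If the target is not achieved, a second reminder by phone will be conducted approximately 1.5 weeks after the invite was sent out". Here the trigger is the recruitment count.
- At about 3 weeks a further email goes to those who have still not completed.
- Closure: "The recruitment in each target country will be stopped when the target number is reached". Table 4 gives an indicative 30 per country.

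The section also records, for each prescriber, the number of contacts and the date and time of completion.

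Section 9.9.1 says of volunteers that "it is possible that prescribers willing to participate in the study will have the highest awareness of risks". Under web-survey limits, it gives spam filters and unread mailboxes as part of the reason for phoning healthcare professionals as well.

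**The concern.** Drawing invitees at random protects against selection at invitation. It does not protect against selection at response, and that is where a stop-at-target rule acts. If a country reaches its number from the first email and the one-week reminder, randomly selected prescribers who would have answered the phone call or the three-week email are left out. The phone call that section 9.9.1 presents as an answer to missed emails may then never be made.

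Success on awareness, knowledge and self-declared behaviour is judged against 80% of prescribers (section 9.7.2.2, Assessment of success). If those who answer early are better informed than those who need chasing, the observed proportion is too high, in the direction that favours declaring the measures effective.

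There is also a smaller effect on reporting. Section 9.7.2.1 places everyone who did not respond in R. Invitees cut off before their reminders would count there, lowering the reported response rate and raising the refusal rate for a reason unrelated to refusal.

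**Working it through.** **The plan's own figure.** Section 9.5.1 uses n = P(1−P)z²/e². With P = 0.5, z = 1.96 and e = 0.08, n = 0.25 × 1.96² / 0.08² = 150.06, which reproduces 150, or 5 × 30. The half-width is 8.0 points at P = 50% and 6.4 points at P = 80%. Both cover sampling error only.

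**When the stopping rule selects.** The protocol gives neither a release size nor an expected response rate, so the rates here are assumptions. If a fraction r of invitees would eventually complete, 30 questionnaires need 30/r invitations: 600 at r = 5%, 300 at 10%, 150 at 20%. Early responders crowd out later ones only when more than this are invited at once. At r = 10%:

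- 300 invited: 300 × 0.10 = 30 eventual completers, so none is shut out.
- About 429 invited: about 43 eventual completers, of whom 13 (30%) are shut out.
- 600 invited: 60 eventual completers, of whom 30 (50%) are shut out. The reported response rate is 30/600 = 5%, against 60/600 = 10% under full follow-up.

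**Size of the bias.** Suppose the target is filled entirely by early responders. Relative to all eventual responders,

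bias = (share of late responders) × (early success − late success).

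This is an upper illustration, because it puts no late responder in the sample. The low end is 0.30 × 10 = 3 points and the high end is 0.50 × 20 = 10 points. The late shares and the gaps are assumed; the documents give neither.

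**Effect on the 80% criterion.** Take true success of 75% among all eventual responders, an unweighted sample of 150 and the same shift in every country. The exact binomial chance of observing at least 120/150 is:

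| Late share | Gap (points) | Shift (points) | Chance of reaching 80% |
|---|---|---|---|
| none shut out | – | 0 | 0.09 |
| 30% | 10 | 3 | 0.32 |
| 50% | 10 | 5 | 0.55 |
| 30% | 20 | 6 | 0.67 |
| 50% | 20 | 10 | 0.96 |

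**Whether anything planned would catch it.**

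- The weights in section 9.5.3 vary by country and target population. They cannot change the mix of early and late responders within a country.
- The comparison in section 9.9.1 sets participants against non-participants on characteristics such as country, specialty, years of practice and gender. It does not look at awareness or knowledge.

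**The case against.** The strongest reply is that the selection is conditional on something the protocol does not say. Rolling random enrolment, as section 9.2.4 describes it, fits small successive releases at least as well as one large mailing. The protocol also expects slow recruitment: low response (section 9.4.7), screening of invitees for recent weekly methotrexate prescribing (9.2.1.1), fieldwork that can be extended beyond 12 weeks (9.2), 3 to 5 contacts before a prescriber counts as unreachable (9.2.4.1), and booster recruitment in countries that have already met their minimum (9.2.4.4). If the target fills slowly, all the reminders run and slower responders come in. That stands, and it is why the point is put conditionally.

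Four stronger readings are tempting, and the documents do not support them:

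- A reader might infer that the sample will consist of the quickest volunteers. That depends on the unstated release size.
- A reader might infer that the protocol itself suspects early responders of being the most aware. Section 9.9.1 speaks of willingness to take part and says nothing about speed.
- A reader might infer that countries with long lists would be chased less and that country comparisons are therefore distorted. The documents give no list sizes; Table 2 shows sales shares.
- A reader might infer the same fault in every panel. The reminders for pharmacists (9.2.4.2) and for patients recruited by M3 Global Research (9.2.4.3) carry no target condition. Only the GLocalMind patient enrolment, for Sweden and Poland, repeats the conditional call.

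Ordinary volunteer bias is disclosed in section 9.9.1 and would remain under any stopping rule. What the reply does not remove is that a large single mailing is permitted, that section 9.2.4.1 gives two different triggers for the phone call, and that closing at the target can cut off invitees in mid-sequence.

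**Conclusion.** The point holds in conditional form. Section 9.2.4.1 contradicts itself on when a prescriber is phoned. Its count-based trigger, together with closure at the target, can weight the sample towards early email responders. Whether it does depends on how many are invited at once, which is not stated. An upward bias needs the further assumption that early responders are more aware, which extends the remark about willing participants in section 9.9.1.

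The size is unknown. The 3 to 10 points rest on assumed inputs and on a sample with no late responders, so they illustrate an upper case and are not an estimate. A shift within that range could still decide the result when true success lies a few points below 80%, and the planned interval would not reflect it. The effect through R concerns the participation rates only.

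**What to change.** 1. In section 9.2.4.1, reconcile the two phone triggers so that the phone reminder depends on individual non-completion. Do the same for the target-conditional call under GLocalMind in section 9.2.4.3.
2. State that random invitations are released in batches, that every released prescriber receives the full stated contact sequence, and that all their completed questionnaires are accepted. Close a country at the end of a batch and not at the 30th questionnaire.
3. Report success by number of contacts or by completion time. Section 9.2.4.1 already records both, so no new data are needed, and the detail can sit in the SAP.

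The cost is more reminder calls, compensation for a few questionnaires above 30, and tighter scheduling. The sequence runs about 3 weeks, so allowing 3 to 4 weeks per batch, three batches take 9 to 12 weeks. That is most or all of the planned 12 weeks, which section 9.2 allows to be extended. Modest overshoot in one country is handled by the country weights in section 9.5.3.

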#### 9.2.4.2 Pharmacists

Pharmacists will be recruited by IQVIA's trusted and assessed vendor, M3 Global Research, from the vendor representative panel. As in the prescribers' surveys, pharmacists will be first contacted by email, then by phone if they do not respond to the email. Their recruitment will be done as follows:

The sampling of pharmacists will follow a randomised sampling method which
ensures the representativeness of the population being reached in order to limit
selection bias which is commonly found in opportunistic selection method.
However, only pharmacists who consent will participate, which brings some degree
of selection bias that cannot be ruled out.

Template No.: RWI\_TP\_EPI0016 Revision 1 Reference: RWI\_WI\_EPI0005

Protocol/Study No: SC02 EMA/2018/19/PE

Page 33 of 92

- The M3 Global Research team will randomly contact pharmacists by emails or phone
  calls when needed, according to their sub-groups (see Section 9.2.1.2 for further
  details on pharmacist selection). Survey background and objectives, the contact
  information for questions, and the proposed compensation will be explained at this
  stage.
- If they agree to participate in the survey, they will receive a link to access the survey and the instructions for web questionnaire completion.
- If the questionnaire is not completed in the IQVIA Primary Intelligence electronic data capture (EDC) system, the pharmacists will be sent regular email/phone reminders.
- The M3 Global Research telephone team can call the pharmacists if they see that they get stuck during the course of completing the survey, or if they stop for any reason they might provide technical help or other advice. Pharmacists will also have the option to contact M3 directly if they need support. These interactions cannot be scripted.
- A screening log is maintained to follow-up the inclusion of pharmacists in the survey over time.

If necessary, i.e. if the target number of responders is still not reached, recruitment will continue to achieve the targeted study sample size. A pharmacist will be considered unreachable if he/she has been contacted between 3 and 5 times without any answer being received. The number of pharmacists that are eligible for inclusion in the study and the survey response rate will be monitored regularly.

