# **9.2.4.3** *Patients*

# Patient enrolment by M3 Global Research:

Patients in Germany, France and Greece will be recruited by IQVIA's trusted and assessed vendor – M3 Global Research, from the vendor representative panel. As in the prescribers' surveys, patients will be first contacted by email, then by phone if they do not respond to the email. Their recruitment will be done as follows:

- The sampling of patients will follow a randomised sampling method which ensures
  the representativeness of the population being reached in order to limit selection bias
  which is commonly found in opportunistic selection method. However, only patients
  who consent will participate, which brings some degree of selection bias that cannot
  be ruled out.
- The M3 Global Research team will randomly contact patients by emails or phone calls when needed, according to their sub-groups (see Section 9.2.1.3 for further details on patient selection). Survey background and objectives, the contact

Template No.: RWI\_TP\_EPI0016 Revision 1 Reference: RWI\_WI\_EPI0005

Protocol/Study No: SC02 EMA/2018/19/PE

Page 34 of 92

information for questions, and the proposed compensation will be explained at this stage.

- If they agree to participate in the survey, they will receive a link to access the survey and the instructions for web questionnaire completion.
- If the questionnaire is not completed in the IQVIA Primary Intelligence EDC system, the patients will be sent regular email/phone reminders.
- The M3 Global Research telephone team can call the patients if they see that they get stuck during the course of completing the survey, or if they stop for any reason they might provide technical help or other advice. Patients will also have the option to contact M3 directly if they need support. These interactions cannot be scripted.
- A screening log is maintained to follow-up the inclusion of patients in the survey over time.

If necessary, i.e. if the target number of responders is still not reached, recruitment will continue to achieve the targeted study sample size A patient will be considered unreachable if he/she has been contacted between 3 and 5 times without any answer being received.

The number of patients that are eligible for inclusion in the study and the survey response rate will be monitored regularly.

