# Patient enrolment by GLocalMind:

Patients in Sweden and Poland will be recruited by IQVIA's trusted and quality assessed vendor – GLocalMind, from the vendor representative partner panel.

Patients will be first contacted via both email and GLocalMind's panellist member app (linked to their panel portal), then by phone if they do not respond to the email and app. Their recruitment will be done as follows:

- The sampling of patients will follow a randomised sampling method which ensures
  the representativeness of the population being reached in order to limit selection bias
  which is commonly found in opportunistic selection method. However, only patients
  who consent will participate, which brings some degree of selection bias that cannot
  be ruled out.
- The GLocalMind team will randomly contact patients by emails or via their app when needed, according to their sub-groups. Survey background and objectives, the contact information for questions, and the proposed compensation will be explained at this stage.
- If they agree to participate in the survey, they will receive a link to access the survey and the instructions for web questionnaire completion.
- If the questionnaire is not completed, the patients will be sent a reminder by email one week after the invite was sent out.

Template No.: RWI\_TP\_EPI0016 Revision 1 Reference: RWI\_WI\_EPI0005

Protocol/Study No: SC02 EMA/2018/19/PE

Page 35 of 92

- If the target is not achieved, a second reminder by phone will be conducted approximately 1.5 weeks after the invite was sent out.
- The GLocalMind telephone team can call the patients if they see that they get stuck during the course of completing the survey, or if they stop for any reason they might provide technical help or other advice. Patients will also have the option to contact GLocalMind directly if they need support. These interactions cannot be scripted.
- A screening log is maintained to follow-up the inclusion of patients in the survey over time.

If necessary, i.e. if the target number of responders is still not reached, recruitment will continue to achieve the targeted study sample size A patient will be considered unreachable if he/she has been contacted between 3 and 5 times without any answer being received.

The number of patients that are eligible for inclusion in the study and the survey response rate will be monitored regularly.

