#### 9.6.1 Data Entry/Electronic Data Capture

The data will be self-entered by the participating prescriber, pharmacist, or patient.

The survey will be conducted according to the SOPs of IQVIA Primary Intelligence and IQVIA Real World Evidence Solutions. Data will be collected using an EDC system (Merphin) developed following a full validation process. A rigorous System Development Life Cycle is used for validation that complies with internal IT SOPs of Primary Intelligence (IQVIA).

Template No.: RWI\_TP\_EPI0016 Revision 1 Reference: RWI\_WI\_EPI0005

Protocol/Study No: SC02 EMA/2018/19/PE

Page 43 of 92

Unit testing and formal validation will occur on all appropriate systems and components during the build stage. The internet-based repository will be used to store survey data and other relevant programme information. Questions are programmed to ensure that they are asked in the appropriate sequence. Skip patterns are clearly indicated. Respondents cannot go back to a question once the question has been answered and cannot skip ahead without answering the previous question. Programming will be reviewed by Quality Control and simulated users (User Testing) prior to implementation.

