## 9.8.3 Safeguards, security and traceability of contacts

Operators of the call centre specialised in health surveys will be assigned to the project and trained on the survey methodology prior to fieldwork. The email contacts will be captured in the internal IQVIA and vendor booking systems.

Participating prescribers/pharmacists/patients will access the online survey via a secure link. This link is unique to each HCP/patient.

The answers provided will be collected in an anonymous way.

Data will be recorded in a central database and tracked using an audit trail. The system will enable retrieving all introduced data at any time and will include security elements to prevent anyone other than authorised staff from accessing data. Each user will have a specific profile which will limit his/her use of the database. A copy of the database and the application files will be made outside the server housing the web-based study. These copies for security purposes will be periodically made and stored outside this server.

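### The protocol lets vendor phone staff give undefined, unscripted and unflagged advice during the pharmacist and patient questionnaires, which could bias knowledge success; restricting help to technical matters is a cheap improvement

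*Protocol*

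**What the plan says.** **Pharmacists (9.2.4.2).** The vendor's telephone team can call a pharmacist seen to be stuck partway through the survey, and "if they stop for any reason they might provide technical help or other advice". Pharmacists may also contact the vendor themselves. The section then states that such exchanges cannot be scripted.

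**Patients, first vendor (9.2.4.3; Germany, France, Greece).** The same rule applies: "they might provide technical help or other advice. Patients will also have the option to contact M3 directly if they need support". The bullet ends "These interactions cannot be scripted".

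**Patients, second vendor (9.2.4.3; Sweden, Poland).** The same again: "The GLocalMind telephone team can call the patients if they see that they get stuck during the course of completing the survey", with the same scope of help, and "Patients will also have the option to contact GLocalMind directly if they need support. These interactions cannot be scripted".

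**Prescribers (9.2.4.1).** The internal field team supports prescribers who get stuck or stop, and "they will provide technical help". A free phone number is also offered. No other kind of help is named.

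**What the scores decide.** Section 9.7.2.2 treats 80% successful respondents on each outcome as the mark of effective risk minimisation. Annex 5.2 sets the pharmacist knowledge pass mark at 8 of 10, and Annex 5.3 sets the patient pass mark at 20 of 25.

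**Related safeguards.** Section 9.8.3 says call-centre operators are "trained on the survey methodology prior to fieldwork". Section 9.6.1 says "Respondents cannot go back to a question once the question has been answered". The vendors' screening log follows inclusion over time; it is not described as recording help given.

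**The concern.** The knowledge questions are meant to measure what respondents know unaided. The protocol otherwise protects this: answers are locked once given, response options are randomised (9.8.1), and section 9.9.1 worries that respondents may look answers up online. Telephone advice during completion is a similar threat, arising from the study's own support staff, and section 9.9 does not mention it.

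Three features combine. The permission goes beyond technical help without saying how far. The protocol disclaims control over what is said. Nothing in sections 9.6 to 9.9 marks the questionnaires concerned. If some advice did touch the content of a question still open, some respondents could pass who would otherwise have failed, and knowledge success among pharmacists or patients would be overstated. Without a flag made during fieldwork, nobody could later measure or remove the effect.

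**Working it through.** **1. The plan's own figure.** Section 9.5.1 uses n = P(1−P)Z²/e². With P = 0.50, Z = 1.96 and e = 0.08, n = 0.25 × 3.8416 / 0.0064 = 150.06, which matches the stated 150. The sample size is not in question; it fixes the number of respondents behind each verdict.

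**2. Help allowed, side by side.**

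| Survey | Help named | Scripted | Assisted questionnaires flagged |
|---|---|---|---|
| Prescribers (9.2.4.1) | technical | not stated | not stated |
| Pharmacists (9.2.4.2) | technical or other advice | cannot be | not stated |
| Patients, both vendors (9.2.4.3) | technical or other advice | cannot be | not stated |

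Since technical help is named separately, 'other advice' must mean something more. Nothing says what, and nothing excludes the content of questions.

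**3. How many changed results reach the threshold.** 80% of 150 is 120. Taking an unweighted count, the number of respondents who must move from fail to pass is (0.80 − p) × 150:

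- p = 0.78: 0.02 × 150 = 3
- p = 0.75: 0.05 × 150 = 7.5, so 8
- p = 0.70: 0.10 × 150 = 15

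**4. Chance of meeting the threshold.** This is the exact binomial tail P(X ≥ 120 | 150, p). The protocol gives neither the share helped nor the share whose result changes, so the shifts below are assumptions.

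| True success | No help | 2% of respondents moved from fail to pass | 5% moved |
|---|---|---|---|
| 0.75 | 9.1% | 22.1% (p = 0.77) | 54.9% (p = 0.80) |
| 0.78 | 31.6% | 54.9% (p = 0.80) | 86.1% (p = 0.83) |

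These columns are an upper case: everyone helped was failing and then passes. If help is unrelated to pass or fail status, and every helped failer passes, then helping 5% of respondents at p = 0.75 gives 0.75 + 0.25 × 0.05 = 0.7625 and a chance of 16.3%. If all help is technical, every row stays at its no-help value.

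**5. One supplied answer, for one respondent.** Assume independent items, each answered correctly with probability π. Supplying one answer replaces P(X ≥ 8 | 10, π) by P(X ≥ 7 | 9, π) for a pharmacist, and P(X ≥ 20 | 25, π) by P(X ≥ 19 | 24, π) for a patient.

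| π | Pharmacist | Patient |
|---|---|---|
| 0.60 | 16.7% → 23.2% | 2.9% → 4.0% |
| 0.75 | 52.6% → 60.1% | 37.8% → 42.2% |
| 0.80 | 67.8% → 73.8% | 61.7% → 65.6% |
| 0.85 | 82.0% → 85.9% | 83.8% → 86.1% |

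The gain depends on π and is small for a patient who knows little. No overall bias can be computed from this without the share helped, which is unknown.

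The 10-point pharmacist total needs its own check: Annex 5.2 gives Q5 four sub-questions but keys five answers.

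**The case against.** The strongest reply is that the protocol nowhere says staff discuss or supply answers. The support bullet sits under study enrolment, between the reminders and the screening log, and reads naturally as drop-out prevention. Respondents are described as stuck while completing the survey or stopping for any reason, not as stuck on a question. Most scored knowledge items are agree/disagree statements, so someone who does not know can still click and move on. This stands: contamination is possible under the wording but not established by it.

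The mitigations count for something but do not close the gap. Training on survey methodology is not a rule about content. Locking protects answers already given, not a question still open.

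The prescriber contrast is also softer than it looks. Section 9.2.4.1 names technical help but does not expressly exclude anything else. It shows that a narrower wording was available, not that content help is barred there.

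A reader might infer more than the text supports:

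- *That results become non-comparable between surveys or countries.* Section 9.7.2.2 analyses the three groups separately, the support wording is the same for both patient vendors, and one vendor recruits all pharmacists.
- *That awareness and self-declared behaviour are affected in the same way.* Those items ask about the respondent's own experience or practice, which a caller is unlikely to know.
- *That the bias can be put at a definite number of points.* Any such figure rests on an assumed share helped and assumed item probabilities.

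**Conclusion.** The point holds as a weakness in the stated rule. Sections 9.2.4.2 and 9.2.4.3 permit advice that is undefined, unscripted and unflagged during a self-completed test with fixed pass marks and an 80% verdict. If that advice reaches question content, knowledge success could be biased. Upward is the most plausible direction, assuming that advice on content tends to be correct.

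The size is unknown: zero if all help is technical, and otherwise dependent on how many respondents are helped and how many results change. The threshold counts show only that the verdict is sensitive when true success lies just below 80%: 3 of 150 at 78%, 8 at 75%. They assume equal weights, whereas section 9.5.3 prefers weighted results, under which the number could be smaller or larger depending on country. At 70% it would take 15, which makes a changed verdict much less likely. This is a cheap improvement, not a must-fix.

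**What to change.** 1. In 9.2.4.2 and in both vendor parts of 9.2.4.3, delete 'or other advice'.
2. State in all three surveys, including 9.2.4.1, that support is technical only. Replace the sentence that the exchanges cannot be scripted with a standing instruction not to discuss the content, meaning or answer of any question.
3. Flag each questionnaire completed after a support contact, whether the staff or the respondent began it. The screening log already kept by the vendors can carry the field for pharmacists and patients; section 9.2.4.1 already records the number of contacts with each prescriber. This has to be done during fieldwork, since it may not be recoverable afterwards.
4. Repeat the knowledge success proportion without the flagged questionnaires, in the protocol or in the SAP.

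The cost is a few words in three places, one line in the staff briefing, one log field and one repeated table. The downside is that a few respondents who get stuck may not finish.
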